1.1 Study design

This is a multicenter, prospective study involving Cw6-negative and Cw6-positive patients affected by moderate to severe chronic plaque psoriasis.

The study has four periods: a screening period consisting of two visits (pre-screening and screening), an induction period of 4 weeks, a maintenance period of 20 weeks and an extension period of 48 weeks. The schematic of study design is given in Figure 1.1-1 (for Core phase) and in Figure 1.1-2 (for Extension phase) below.

At pre-screening (day -28), patients will be centrally assessed for Cw6 positivity or negativity and stratified into two cohorts (Cw6-negative and Cw6-positive patients). Both patients and investigators will be blinded to the results with respect to Cw6. At the same time 308-TNF α polymorphism will be centrally determined.

After a full screening visit, each eligible patient will be treated according to an induction regimen of two injections of secukinumab 150 mg a week for five weeks starting at baseline (week 0), followed by a maintenance period of one treatment (two injections) per month. At week 16, patients achieving a PASI 50 response will be eligible to continue on secukinumab for an additional 8 weeks. After a total of 24 weeks, willing patients reaching at least a PASI 75 response will enter an extension treatment period of up to 48 weeks. The total duration of the study, including the extension period, is therefore of 72 weeks. For all summaries of "by phases" analyses, total number of patients (N) for extension phase will be the number of patients who have entered the extension. All percentages in extension phase will be based on this N.

Primary analysis time point

The primary analysis will be performed at 16 weeks, and thereafter for up to 72 weeks.

Planned number of patients

The study plans to enroll about 406 adult men or women, of which 365 are evaluable patients, diagnosed with moderate to severe chronic plaque psoriasis for at least 6 months. The patients must be candidates for systemic therapy and may be treatment naïve or have failed to respond to other systemic therapy (including cyclosporine, methotrexate, psoralen combined with ultraviolet A (PUVA) or to an anti-TNFa (or is intolerant and/or has a contraindication to these). The study plans to involve approximately 50 centers. The extension phase will include approximately 306 of the patients initially enrolled in the core study.

Interim analyses

Novartis

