2.1.1 General definitions

2.1.1.1 Study treatment: Study treatment refers to:

Secukinumab 300 mg (two s.c. injections of secukinumab 150 mg).

2.1.1.2 Study treatment start and end date:

Study treatment start date is defined as the first date when a non-zero dose of study drug is administered and recorded on the Dose Administration Record (DAR) CRF page. Similarly, study drug end date is defined as the last date when a non-zero dose of study drug is administered and recorded on the DAR CRF page.

2.1.1.3 Study day:

Study day will be calculated as (event date – study drug start date + 1 day) for events that occurred on or after study drug start date (e.g.visit, lab samples, AEs). For events prior to study drug start date (e.g., an adverse event occurred before the start of first dose), study day will be negative and calculated as (event date – study drug start date). Note that study drug start date is study day 1 and the day before study drug start date is study day -1 (i.e. no study day 0).

Due to the study drug dosing schedule, one month will be considered as 28 days. Time from events prior to the start of study drug, e.g., time since diagnosis, is calculated as the difference between the start date of study drug and the date of prior event.

Note that, the first dose day is Day 1, and the day before the first dose day is counted as Day - 1 (not Day 0).

2.1.1.4 Baseline and post baseline:

In general, a *baseline* value refers to measurement corresponding to week 0 assessment. A post-baseline value refers to a measurement taken after week 0 assessment.

Change from baseline will only be summarized for patients with both baseline and postbaseline unless stated otherwise, and it will be calculated as:

post-baseline value – baseline value

Correspondingly, percentage change will be calculated as:

100 * (post-baseline value – baseline value) / baseline value

For DLQI, In case baseline value is zero (0), percentage change will be calculated as (post-baseline value -0)*100 %.

2.1.1.5 Study periods:

The study has four periods: a screening period consisting of two visits (pre-screening and screening), an induction period of 4 weeks, a maintenance period of 20 weeks and an extension period of 48 weeks.

For analyses which will be done by phases (i.e., Core and Extension separately) the following rules will be applied to summarize the data.

For spontaneous data (CM, AE) as below:

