• For the subjects who did not enter Extension Phase, all events/medications belongs to Core Phase

- · If event/medications start date is on or before visit date of E0, then APERIOD=Core Phase
- If event/medications start date is after visit date of E0, then APERIOD=Extension Phase.

For Planned data (i.e., Visit wise, all safety and efficacy) will be derived as below:

- · Visits before E0 will belong to Core Phase
- · Visits on or after E0 will belong to Extension Phase

Basically reporting will be done for visit assessment data in extension phase which is collected on or after ICF is signed for extension phase.

The above rules are irrespective of whether V12 visit date and E0 visit date are same or different.

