2.7.1 Secondary endpoints

The analyses of all secondary efficacy endpoints will be based on the ITT.

Refer to Table 1.2-1 of Section 1 for the list of secondary endpoints.

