2.7.2 Statistical hypothesis, model, and method of analysis

PASI

Summary statistics for PASI 50, PASI 75, PASI 90, PASI 100 response by visit will be presented with absolute and relative frequencies. Confidence intervals for response rates will be derived as well, based on the score method including continuity correction (Newcombe 1998). The summaries will be done using prevalence (observed data), LOCF and NRI approaches.

Summary statistics will be provided for absolute PASI scores and for percent changes from baseline by visit and cohort using prevalence, and LOCF approches. Graphical representations will also be provided on ITT set.

The two cohorts will be compared on PASI scores (absolute change from baseline) using MRMM model with LOCF, prevalence and MI approaches on ITT set.

PASI Changes vs baseline: Linear Mixed Model for Repeated Mesurements (MMRM):

In order to evaluate if there is a differences between cohorts in PASI changes at each time point vs week 0, a longitudinal analyses of changes from baseline will be performed over the course of the study including all the measurements assessed at each time point for the ITT population using a linear mixed model for repeated measurements (MMRM). An unstructured

covariance matrix for the repeated measures within each patient will be applied in the analysis, if the model does not converge, compound symmetry will be used. The explanatory variables in the longitudinal model include cohort, visit, cohort-by-visit interaction, missing data pattern (completers, missing one assessments, missing two assessments, missing three assessments, etc till all visits in the overall study period), propensity score, and corresponding baseline (week 0). The two cohorts will be compared at each time point by reporting a point estimate, p-value, and 95% confidence interval for the treatment difference, based on least squares means.

The propensity score analysis will consider the following baseline factors: age, geographical region (i.e. north vs south vs central), BMI categories (<25 vs >=25), waist circumference, smoking status (Yes vs No), metabolic syndrome (yes vs no), previous PsO therapy (naïve vs previous systemic therapy vs previous biologic therapy), PsA (yes vs no), age at diagnosis of psoriasis, IGA mod 2011 (severe, moderate, mild) as strata factors. This approach allows us also to maximize the analysis model adding only one variable instead of several ones.

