2.8 Safety analyses

All the safety analysis will be performed on Safety set by study phase (i.e. CORE and Extensions) and overall.

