2.8.3 Laboratory data

Summary statistics of laboratory data and absolute and changes from baseline will be provided by visit and cohort. Summaries will be provided on the following laboratory test and their parameters;

Hematology: Hemoglobin, hematocrit, red blood cell count, white blood cell count with differential (e.g. neutrophils, basophils, eosinophils, monocytes, lymphocytes) and platelet count.

Chemistry: Albumin, alkaline phosphatase, total bilirubin, bicarbonate/CO2, calcium, cholesterol, chloride, creatinine, CK, GGT, glucose, LDH, inorganic phosphorus, lipase, amylase, magnesium, potassium, total protein, AST, ALT, sodium, triglycerides, urea/BUN and uric acid.

Urinalysis: Specific gravity, pH. Summary table of change from baseline will not be perfomed for specific gravity, since the data captured by sites are in different ranges, which cannot be converted.

hsCRP

Patients with values above (H) or below (L) notable criteria (Table 2.8.3) will be listed and absolute and relative frequencies will be presented by visit and cohort. Laboratory values will be presented for each patient in a data listing with an indication of whether the value is above (H) or below (L) the normal reference range.

Laboratory data will also be summarized by presenting shift tables for each laboratory parameter showing the number and percentage of patients in each cohort with the most extreme post-baseline value that falls outside normal ranges by the classification of value at baseline (H/N/L).

For urinalysis of categorical variables (Glucose, Protein, Blood, WBC, RBC), summary table of number and percentage of patients by cohort and visit will be presented.

Laboratory parameter	Criterion for notable abnormalities
Liver Function and Relat	ted Variables
ALT (SGPT)	> 3 x Upper Limit of Normal (ULN)
AST (SGOT)	> 3 x ULN
Total bilirubin	> 2 x ULN

Table 2.8.3 Clinically notable laboratory abnormalities

Alkaline phosphatase (ALP)	> 2.5 x ULN
Renal Function and Elec	trolyte Variables
Serum Creatinine	> 1.5 x ULN
Potassium	> 6 mmol/L or < 3 mmol/L
Sodium	> 160 mmol/L or < 115 mmol/L
Hematology Variables	
Hemoglobin	\geq 20 g/dL decrease from baseline
Platelet count	< Lower Limit of Normal (LLN)
White blood cell count	< 0.8 x LLN
Neutrophils	< 0.9 x LLN
Eosinophils	> 1.1 x ULN
Lymphocytes	> 1.1 x ULN
Urinalysis Variable	
Protein urine dipstick	++* (*++ is > 100 mg/dL)

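### By-visit notable laboratory and vital-sign percentages in the extension are divided by everyone who entered, so they are understated once entrants have no value at a visit

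*SAP*

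**What the plan says.** SAP 1.1 defines the denominator for by-phase summaries: "total number of patients (N) for extension phase will be the number of patients who have entered the extension". It then adds, with no exception for tables laid out by visit, "All percentages in extension phase will be based on this N".

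SAP 2.8 brings all safety output under that rule: "All the safety analysis will be performed on Safety set by study phase (i.e. CORE and Extensions) and overall". SAP 2.8.3 (notable laboratory values) and SAP 2.8.4.3 (notable vital signs) use the same wording for the tables: "absolute and relative frequencies will be presented by visit and cohort". SAP 2.1.1.5 assigns visit data dated on or after E0 to the extension and names visit-wise safety data among the data covered: "For Planned data (i.e., Visit wise, all safety and efficacy) will be derived as below".

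Protocol Table 6-2 schedules laboratory tests, urinalysis and vital signs at E1 to E4 (weeks 36, 48, 60 and 72). Protocol 5.5.12 allows the sponsor to end the extension once at least 12 weeks have passed, region by region. No imputation is planned for laboratory values or vital signs.

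**The concern.** Everyone who entered is a sound denominator for a question about the whole phase, such as the share of patients with any adverse event. It is the wrong one for a question about a single visit. A patient with no measurement at week 60 cannot be shown to have a notable value at week 60, yet under the rule counts as one of those who did not have one.

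The design makes such gaps likely. Besides ordinary drop-out and missed visits, the sponsor may close the extension by region from about week 36 (24 + 12). Entrants in a closed region are then never due at some or all of the later visits.

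Long-term safety is one of the three stated reasons for the extension. Notable values would look rarer at later visits simply because fewer patients were measured. For safety that is the non-conservative direction. If the share without a value differed between the Cw6 cohorts, the tables would also show a cohort gap that reflects follow-up only.

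**Working it through.** **Inputs from the documents.** Planned entrants: about 306 (Protocol 4, SAP 1.1), given without a derivation. The plan states no figure of its own for this point, so there is none to reproduce. The documents give no share of entrants without a value at a visit and no rate of notable values.

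**Assumptions.** Share without a value at a given extension visit: 10%, 20% or 30%. Notable rate among those measured: 20% or 5%, the same in measured and unmeasured patients.

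**Formula.** Let E be the number entered, m the number with a value at the visit and x the number with a notable value.

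- Observed rate = x / m
- Rate under SAP 1.1 = x / E = (x / m) × (m / E)

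**Numbers with a value.** 306 × 0.90 = 275; 306 × 0.80 = 245; 306 × 0.70 = 214 (rounded).

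| Without a value | m | Observed, 20% case | Printed on 306 | Printed, 5% case |
|---|---|---|---|---|
| 10% | 275 | 55/275 = 20.0% | 55/306 = 18.0% | 0.05 × 275/306 = 4.5% |
| 20% | 245 | 49/245 = 20.0% | 49/306 = 16.0% | 0.05 × 245/306 = 4.0% |
| 30% | 214 | 43/214 = 20.1% | 43/306 = 14.1% | 0.05 × 214/306 = 3.5% |

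The relative understatement equals the share without a value, whatever the rate. In absolute terms it is 2 to 6 percentage points for a 20% rate and 0.5 to 1.5 points for a 5% rate.

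**Cohort gap.** Take a true rate of 20% in both cohorts, with 10% of Cw6-positive and 20% of Cw6-negative entrants lacking a value (assumed). The printed rates are 0.20 × 0.90 = 18% and 0.20 × 0.80 = 16%, a 2-point gap with no true difference. With 10% against 30%, the gap is 18% − 14% = 4 points.

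**Which visits.** E1 is at week 36, the earliest point at which closure can take effect, so closure acts mainly on E2 to E4. Missed visits and drop-out can also affect E1.

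**The case against.** **The reader can recompute.** SAP 2.3.1 plans a count of patients at each visit. SAP 2.8.3 and 2.8.4.3 ask for absolute as well as relative frequencies and for summary statistics by visit, which under SAP 2.1 include n. A careful reader could therefore rebuild the observed rate. This stands as mitigation, but the percentage printed in the table would still be wrong for the visit it is labelled with.

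**The size is assumed.** This also stands. For uncommon abnormalities the absolute shift is small, as the 5% case shows.

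**By-phase may not have been meant to cover by-visit tables.** For safety the text is against this. SAP 2.8 makes all safety analyses by-phase, and SAP 2.1.1.5 lists visit-wise safety data under its by-phase rules.

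**A stronger reading: PASI response too.** A reader might infer that PASI rates up to week 72 are also divided by all entrants, because SAP 1.1 refers to all percentages and SAP 2.1.1.5 mentions visit-wise efficacy. The more specific text does not support this. The SAP 2.1.1.5 rules are conditional: "For analyses which will be done by phases (i.e., Core and Extension separately) the following rules will be applied to summarize the data". SAP 2.7.1 says "The analyses of all secondary efficacy endpoints will be based on the ITT", and SAP 2.7.2 says "Summary statistics for PASI 50, PASI 75, PASI 90, PASI 100 response by visit will be presented with absolute and relative frequencies", to be done on observed data, with LOCF and with NRI. SAP 2.5.4 also names observed data for the primary variable. The sample PROC FREQ code in SAP 5.4.1 and 5.4.3 runs by visit and by default leaves out missing responses. Nor can it be inferred that a printed PASI rate would fall outside its own confidence interval. That would need a percentage on all entrants set beside an interval on measured patients only, and no passage asks for that pairing.

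**Conclusion.** The point holds for by-visit percentages of notable laboratory values and vital signs in the extension tables. Followed as written, SAP 1.1 with 2.8, 2.8.3 and 2.8.4.3 shrinks each of these by the factor assessed/entered. A 20% rate would print as about 18%, 16% or 14%, and a 5% rate as about 4.5%, 4.0% or 3.5%, if 10%, 20% or 30% of 306 entrants had no value. The shares and rates are assumptions; the shrinkage factor is not.

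The effect is confined to descriptive safety percentages. The week-16 test, the sample size and the models are untouched, and the entrant N remains right for phase-level incidence.

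For PASI and IGA response only a clarification is needed. A related gap is the status of patients whose extension the sponsor closes. SAP 2.5.3 withholds imputation from extension patients who finish the study ahead of week 72, which may well be aimed at closure but does not say so. The first paragraph of Protocol 5.5.12 has patients handled as early withdrawals if the study is terminated, while its paragraph on the extension gives no status. The two documents need to be reconciled on this. It is not evidence of an error in the PASI analysis.

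**What to change.** 1. In SAP 1.1, limit the entrant N to phase-level extension tables that are not presented by visit, such as patients with any adverse event.
2. In SAP 2.8.3 and 2.8.4.3, base by-visit percentages of notable values on the patients with a value in that visit window, and print n/m by cohort.
3. As a clarification, state that the SAP 1.1 N does not apply to the by-visit PASI and IGA response summaries, which use observed or planned imputed values.
4. As a clarification, state in SAP 2.5.3 whether closure of the extension by the sponsor counts as completing the study before week 72, and align this with Protocol 5.5.12.

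The cost is a few sentences in the SAP and no new data. The small drawback is that denominators then vary from visit to visit, which is why they should be printed.

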1.2 Study objectives and endpoints

Table 1.2-1 **Objectives and related endpoints**

Objective	Endpoint
Primary objective	
To evaluate the clinical response in Cw6- negative and Cw6-positive patients treated with secukinumab 300 mg with respect to the Psoriasis Area Severity Index (PASI) 90 response rate after 16 weeks, and	PASI 90 response after 16 weeks of treatment, defined as the achievement of \geq 90% improvement (reduction) in PASI score after 16 weeks of treatment compared to baseline and thereafter for

thereafter for up to 72 weeks.	up to 72 weeks.			
Secondary objective				
To compare the proportion of responders to PASI 50/75/90/100 between cohorts at each time point.	Proportion of responders to PASI 50/75/90/100 at each time point.			
To compare the mean changes vs baseline in the Investigator's Global assessment (IGA) mod 2011 between cohorts at each time point.	Change from baseline in IGA mod 2011 between Cw6-negative and Cw6-positive at each time point.			
To compare time to reach PASI 90 between cohorts.	Time to PASI 90 response between Cw6- negative and Cw6-positive.			
To compare time to reach PASI 75 between cohorts.	Time to PASI 75 response between Cw6- negative and Cw6-positive.			
To evaluate the quality of life by means of the Dermatology Life Quality Index (DLQI) in all patients at each time point.	Change from baseline in DLQI at each time point.			
To evaluate anxiety and depression using the Hospital Anxiety and Depression Scale (HADS) in all patients at each time point	Change from baseline in HADS at each time point.			
To evaluate the correlation between HADS and PASI in all patients.	Correlation coefficient between HADS and PASI.			
To evaluate changes from baseline in weight, BMI and waist in all patients at each time point.	Change from baseline in weight, BMI and waist at each time point.			
To compare safety and tolerability between cohorts during the 24 weeks, and then during the whole study period.	Overall safety, as measured by frequency and severity of adverse events and changes in laboratory, vital signs, ECG values and chest X-ray from values baseline.			
To evaluate the amount of resources used during the study in comparison with the 6 months prior to the beginning of the study.	Health resources use will be conducted considering the comorbidities (such as anxiety and depression), PsO medical history, concomitant medication and adverse event.			

2 Statistical methods

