Height, weight, BMI and waist		X	X							X		X
Vital signs		X	X				X	X	X	X	X	X
PASI		X	X	X	X	X	X	X	X	X	X	X
IGA mod 2011		X	X	X	X	X	X	X	X	X	X	X
Lab assessments: hematology and chemistry ¹		X	X				X	X	X	X	X	X
hsCRP			X							X		X
HCV, HBV* and HIV tests (within 6 months)		X										
Serum pregnancy test		X										
Urinalysis		X								X		X
Secukinumab administration			X	X	X	X	X	X	X	X	X	X
DLQI			X							X		X
HADS			X							X		X
Cw6 centralized determination	X											
ECG (within 6 months)		X										
Chest X-ray (within 6 months)		X										
Study completion												X [^]
Concomitant medication												As needed
Adverse events												As needed
Liver events												As needed

¹Hematology: Hemoglobin, hematocrit, red blood cell count, white blood cell count with differential (e.g. neutrophils, basophils, eosinophils, monocytes, lymphocytes) and platelet count; Chemistry: Albumin, alkaline phosphatase, total bilirubin, bicarbonate/CO₂, calcium, cholesterol, chloride, creatinine, CK, GGT, glucose, LDH, inorganic phosphorus, lipase, amylase, magnesium, potassium, total protein, AST, ALT, sodium, triglycerides, urea/BUN and uric acid.

* Height will be assessed only at screening or at baseline

* HBsAg, HBsAb, HBcAb

[^] End of Study visit for patients not proceeding to the extension treatment period.

Table 6-2 lists all the assessments of the extension phase and indicates with an “x” when the visits are performed.

Patients should be seen for all visits on the designated day but a time window of ± 7 days is allowed.

Table 6-2: Assessment schedule of extension treatment period

Visit	E0*	E1	E2	E3	E4/ End of Extension or PPD
Week (relative to baseline)	24	36	48	60	72
Recommended visit window (days)	±7	±7	± 7	±7	±7
Informed consent	X				
Inclusion/Exclusion criteria	X				
Physical Examination		X	X	X	X
Weight and waist		X	X	X	X
Vital signs		X	X	X	X
PASI		X	X	X	X
IGA mod 2011		X	X	X	X
Lab assessments: hematology and chemistry [†]		X	X	X	X
Urinalysis		X	X	X	X
Secukinumab administration	AS NEEDED				
DLQI			X		X
HADS			X		X
Check self-administration log		X	X	X	X
Dispensing Secukinumab for self-administration at home	X	X	X	X	
Study extension completion					X
Concomitant medication	AS NEEDED				
Adverse events	AS NEEDED				
Liver events	AS NEEDED				

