6.5.3 Height, weight and waist

Height in centimeters (cm) will be measured at visit 2 or 3 only.

Body weight (to the nearest 0.1 kilogram in indoor clothing, but without shoes) and waist will be measured at visits 2, 3 and 12 of the core study and at all four visits of the extension period. BMI will be derived from weight and height results.

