6.5.4.3 Urinalysis

Dipstick measurements for specific gravity, protein, glucose and blood will be performed. WBC and RBC sediments will also be analyzed at visits 2, 10 and 12 of the core study and at all four visits of the extension period.

6.5.4.4 hsCRP

hsCRP will be assessed at visits 3, 10, and 12 of the core study and at all four visits of the extension period.

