6.5.5 Electrocardiogram (ECG), chest X-ray

An ECG and chest X-ray will be required at visit 2 unless performed within the previous 6 months. Adequate documentation (assessment reports, tracking and images as applicable) must be available for previous evaluations to be considered as baseline.

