2.8.4 Other safety data

2.8.4.1 ECG and cardiac imaging data

Summary of normal and abnormal ECG findings at screening will be presented by cohort on Safety set.

Listing will be provided for the normal and abnormal ECG findings at screening on Safety set.

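### Some secondary safety outputs do not match the visit schedule: ECG and chest X-ray change, the urinalysis baseline, urine pH, and week-16 weight and waist

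*SAP*

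**What the plan says.** **ECG and chest X-ray.** The safety endpoint in SAP Table 1.2-1 includes "changes in laboratory, vital signs, ECG values and chest X-ray from values baseline". Protocol 6.5.5 states: "An ECG and chest X-ray will be required at visit 2 unless performed within the previous 6 months". SAP 2.8.4.1 plans this for ECG: "Summary of normal and abnormal ECG findings at screening will be presented by cohort on Safety set". SAP 2.8.4.2 plans the same for chest X-ray.

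**Urinalysis baseline.** SAP 2.1.1.4 says that, in general, a baseline "value refers to measurement corresponding to week 0 assessment", and that change is summarised only for patients with both a baseline and a later value. Protocol 6.5.4.3 gives the core-study timing: "WBC and RBC sediments will also be analyzed at visits 2, 10 and 12 of the core study". Table 6-1 marks urinalysis at the same three visits. Protocol 9.5.2 plans changes from baseline and shift tables under a heading that names urinalysis. SAP 2.8.3 plans shift tables for each laboratory parameter by baseline class (high, normal, low).

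**Urine parameters.** SAP 2.8.3 lists "Urinalysis: Specific gravity, pH", then drops the change summary for specific gravity because sites recorded it in ranges that cannot be converted. The dipstick list in Protocol 6.5.4.3 is specific gravity, protein, glucose and blood.

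**Weight and waist.** Protocol 6.5.3 says weight and "waist will be measured at visits 2, 3 and 12 of the core study". The Table 6-1 row "Height, weight, BMI and waist" is marked at visits 2, 3, 10 and 12. Change in weight, BMI and waist at each time point is a secondary endpoint, and SAP 2.8.4.4 fits an ANCOVA to it at each time point.

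**The concern.** Each of these outputs is promised in one place and lacks scheduled data, a usable baseline or a consistent schedule in another. An endpoint table is often copied into a report or registry entry without the detail behind it. As worded, it implies that cardiac and chest findings were followed after treatment began. For urinalysis, a programmer who applies the SAP's baseline rule literally obtains no baseline, and the change and shift tables come out blank. For weight and waist, whether a week-16 value exists depends on which protocol text a site follows, so the week-16 comparison of cohorts could rest on only some of the sites.

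**Working it through.** The plan gives no figure to reproduce here. The check sets each planned output against the schedule. Table 6-1 was read by counting columns. The same count applied to the hsCRP row gives visits 3, 10 and 12, which matches Protocol 6.5.4.4.

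**1. ECG and chest X-ray**
- Table 6-1: one mark each, at visit 2. An exam from the previous 6 months is also accepted.
- Table 6-2: no row for either.
- Scheduled assessments after baseline: 0 in 72 weeks. No change can be formed, and the SAP's analysis sections plan none.

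**2. Urinalysis baseline**
- Scheduled samples: visits 2, 10 and 12, and E1 to E4. The visit-3 list in Protocol 6.2 has hematology and chemistry but no urinalysis.
- SAP Table 2.1: Screening is day -28 to -4; Baseline is day -3 to day 1.
- Visit 2 is day -14 to -7, wholly inside Screening. Its latest day falls 4 days before the Baseline window opens (-3 - (-7) = 4).
- Scheduled samples in the Baseline window: 0. Scheduled samples after baseline: 2 + 4 = 6.
- The rule in SAP 2.1.1.6 for combining windows does not help. Its example starts at day 2, and SAP 2.1.1.7 refers baseline back to 2.1.1.4.

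| Urine output | Needs a baseline? | Result as written |
|---|---|---|
| Change, specific gravity | Yes | Already dropped by SAP 2.8.3 |
| Change, pH | Yes | Empty |
| Any high/normal/low shift table | Yes | Empty |
| By-visit counts of glucose, protein, blood, WBC, RBC | No | Unaffected |
| Notable urine protein (absolute level) | No | Unaffected |

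**3. Urine pH**
- Protocol list: four dipstick analytes plus WBC and RBC sediment. SAP quantitative list: specific gravity and pH.
- The two share only specific gravity, whose change is dropped. That leaves pH as the one quantitative urine parameter with a planned change, and the protocol does not list it.

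**4. Weight and waist**
- Table 6-1 with Table 6-2: weeks 16, 24, 36, 48, 60 and 72, so 6 time points after baseline.
- Protocol 6.5.3: weeks 24, 36, 48, 60 and 72, so 5.
- The disputed point is week 16, one of the two core-study time points in Table 6-1.
- The conflict also moves a window. SAP 2.1.1.6 combines windows for parameters not taken at every visit. With week 16 scheduled, week 24 covers day 127 to 210. Without it, the same rule would start week 24 at day 2. A value from day 112 could then stand as the week-24 value for a patient with nothing closer to day 168.

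**The case against.** The strongest reply is that these are alignment errors in secondary, mostly descriptive outputs. Much of that stands.

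- **ECG and chest X-ray.** The analysis sections already limit both to screening, and Protocol 9.5.2 plans no change in either, so only one table cell is wrong. That is correct. The cell still states an endpoint that cannot exist and contradicts the SAP's own analysis text.
- **Urinalysis.** A reader might infer that the urinalysis safety data are lost. They are not: the categorical results are counted by visit, and the notable-protein rule needs no baseline. The baseline rule is also hedged as a general one, and Protocol 6.2 collects urinalysis at visit 2 under a heading on baseline characteristics. Using visit 2 is therefore not barred. But no exception is written, so the rule as it stands gives no baseline.
- **pH.** A reader might infer that pH was never collected. The documents do not show that. The eCRF is not available, and the SAP's remark on how sites recorded specific gravity suggests that its authors had seen the captured data. What can be said is that the two lists differ.
- **Weight and waist.** A reader might infer that these changes cannot be derived. They can, at week 24 and throughout the extension, and at week 16 wherever Table 6-1 is followed. The introduction to Protocol section 6 presents that table as the full list of assessments. This is a contradiction, not missing data, and uneven site practice is a risk rather than something the documents show.
- **A general fallback baseline.** It is tempting to replace the baseline rule for all variables. That would let a visit-2 PASI serve in the PASI 90 calculation. Several washouts in Protocol Table 5-1 are 2 weeks before day 1, and visit 2 falls 7 to 14 days before it, so such a score may precede completed washout. PASI is scheduled at visit 3 for everyone, and a week-0 baseline is a sound choice.

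**Conclusion.** The point holds as a set of four mismatches in secondary safety outputs. ECG and chest X-ray have no scheduled assessment after baseline, so their change from baseline cannot be derived. Urinalysis has no scheduled sample in the baseline window, so under the SAP's rule its change and shift summaries would be empty while its by-visit counts remain. Urine pH is in the SAP's list and not in the protocol's. Week-16 weight, BMI and waist rest on conflicting protocol texts; the other five time points do not.

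This assumes that visits take place as scheduled, that the SAP baseline rule is applied as written, and that no eCRF instruction outside these documents settles the urine list or the visit-10 measurements. The PASI 90 primary analysis is not affected, nor are adverse events, hematology, chemistry or vital signs, for which these mismatches do not arise. The corrections should be made because they cost almost nothing and the affected text is wrong as written.

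**What to change.** 1. In SAP Table 1.2-1, remove ECG and chest X-ray from the change-from-baseline endpoint and describe them as screening findings, in line with SAP 2.8.4.1 and 2.8.4.2.
2. In SAP 2.1.1.4, add one sentence for urinalysis only: baseline is the last non-missing value before first dose, normally visit 2. Leave the week-0 PASI baseline as it is.
3. Align the urine parameter lists in SAP 2.8.3 and Protocol 6.5.4.3, either by removing pH from the SAP or by adding it to the protocol list, according to what the eCRF captures.
4. Reconcile Protocol 6.5.3 with Table 6-1 at visit 10, so that week-16 weight, BMI and waist are collected consistently and the SAP windows follow from one schedule.

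The cost is SAP wording and a line or two of protocol text. Items 1 and 2 add no visit or procedure, and item 4 adds none beyond what Table 6-1 already marks. The one downside is a urine baseline 1 to 2 weeks older than a week-0 sample would be.
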